## 3 STUDY DESIGN

This study is a phase II, randomized, open label study of up to 48 weeks of treatment with EBP-994 alone, or in combination with Norvir® and/or Pegasys® in subjects chronically infected with HDV genotype 1. The investigator is free to initiate licensed medications at any time point and decrease the dose of EBP-994 if deemed warranted for GI side effects. The duration of the study for each subject will be approximately 11-55 weeks (up to three week screening period, up to 48 week treatment period and four week safety follow-up period).

The duration of the entire study is anticipated to be approximately 36 months (first subject in to last subject out). Pharmacokinetic sampling will be done at Day 1 and Day 28 of dosing. PK sampling will be conducted only on subjects who have consented to participate in the PK portion of this study. Participation in PK sampling is optional for each subject.

At the Screening Visit, subjects giving written informed consent will have all required evaluations to determine their eligibility to participate in the study. The outpatient screening visit must occur within 21 days of Study Visit 1.

Each eligible subject will undergo 8-16 Study Visits; Screening, Day 1, Day 2, Day 3, Day 7, Day 14, Day 28, then every 4 weeks (total duration depends on assigned treatment group), followed by a Safety Follow-Up Visit, 4 weeks post-treatment. Study drug will consist of EBP-994 alone or in combination with either Norvir® and/or Pegasys®, depending on which group the subject has been randomized to on the Day 1 visit. Moreover, the investigator is free to initiate licensed medications at any time point and decrease the dose of EBP-994 if deemed warranted for GI side effects.

During the intervals between Study Visits, subjects will be free to carry on their usual activities of daily living. Subjects will be instructed to take their study medication at appropriate dosing intervals. Efforts should be made to schedule Study Visits according to the study protocol; however the window for consecutive Study Visits will be  $\pm 2$  days with the exception of Day 2 and Day 3 for which a visit window is not allowed.

Safety will be monitored by assessing vital signs, adverse events, concomitant medications, laboratory and ECG results. ECGs will be conducted and vital signs assessed at each Study Visit.

As with all antiviral medications, a possible effect of EBP-994 is viral resistance. Hepatitis D viral load levels will be measured through quantitative PCR at all Study Visits. Viral mutation analysis and resistance phenotyping will be conducted to assess viral resistance to the study medication. The investigator may terminate the subject from the trial if, in his/her opinion, there is an unacceptable increase in HDV viral load.

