#### **4.3 *Withdrawal Of Subjects***

At any time during the study, a subject may discontinue (i.e., withdraws consent or is no longer willing to participate) or a subject may be withdrawn by the Investigator because of a safety risk, adverse event, or noncompliance. The reason for early withdrawal shall be noted in the appropriate CRF.

The Sponsor has the option to enroll additional subjects to replace subjects who discontinue prematurely.

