# **7 ASSESSMENT OF SAFETY**

## **7.1 Procedures For Recording Adverse Events**

All adverse events encountered during the clinical study will be recorded on the case report form (CRF). An adverse event is defined by the International Conference on Harmonization (ICH) as follows:

- Any untoward medical occurrence in a patient or clinical investigation subject administered a pharmaceutical product and which does not necessarily have a causal relationship to this treatment
- An adverse event (AE) can therefore be any unfavorable and unintended sign (including any abnormal laboratory finding for example), symptom, or disease temporarily associated with the use of a experimental drug, whether or not considered related to the experimental drug

An adverse event is any adverse change from the subject's baseline condition, including any clinical or clinically significant laboratory test value abnormality that occurs during the course of the clinical study after the experimental drug has been utilized, whether the adverse event is considered related to the treatment or not.

All adverse events will be followed until resolution. This may require obtaining clinical blood samples for appropriate laboratory tests until their values return to baseline levels or performing follow-up physical examinations until resolution of identified abnormalities.

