## **7.2 *Withdrawal From Study Treatment Due To Adverse Experience***

Subjects withdrawn from receiving additional study drug due to an adverse experience will be followed by the Investigator until the outcome is determined; additional reports will be provided to the Sponsor or regulatory authorities when requested. Every effort will be made to follow the subject for the full study period as per the schedule of Study Visits.

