## **8.2 *Analysis Populations***

The Safety Population comprises all subjects who are enrolled and receive at least one dose of study drug, and who have at least one post-dosing safety evaluation. All safety endpoints will be analyzed using the Safety Population.

The Per-Protocol Population comprises all subjects who complete at least Study Visit 4, as specified in the protocol. All pharmacodynamic analysis will be conducted using the Per-Protocol Population.

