### **8.6 Pharmacodynamics**

Listings will display viral load data at each period/timepoint collected by subject and these data will be presented graphically. Mean and median levels of the viral load will be calculated at each period/timepoint.

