### **8.9 Missing Data And Data Imputation**

No missing safety or pharmacodynamic data will be estimated.

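### Ending trial participation for an HDV viral-load rise, with no follow-up expressly tied to that stop, lets observed-only later-visit summaries omit virologic failures (a minor fix in a descriptive pilot)

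*Combined protocol and SAP*

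**What the plan says.** **The stopping rule.** Section 3 reads: "The investigator may terminate the subject from the trial if, in his/her opinion, there is an unacceptable increase in HDV viral load". The Protocol Summary (Safety) and section 7.3 carry the same rule. None of the three places gives a threshold or says what happens to measurement afterwards. HDV viral load is among the primary objectives in section 2.

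**Follow-up after a stop.** Section 7.2 covers subjects taken off study drug because of an adverse experience, and for them: "Every effort will be made to follow the subject for the full study period as per the schedule of Study Visits". For withdrawals in general, section 4.3 asks only this: "The reason for early withdrawal shall be noted in the appropriate CRF". It then adds: "The Sponsor has the option to enroll additional subjects to replace subjects who discontinue prematurely".

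**The analysis.** Section 8.6 plans by-subject listings, graphs and a summary: "Mean and median levels of the viral load will be calculated at each period/timepoint". Section 8.9 adds: "No missing safety or pharmacodynamic data will be estimated". The population is set in section 8.2: "The Per-Protocol Population comprises all subjects who complete at least Study Visit 4, as specified in the protocol". Visit 4 is Day 3, so a subject removed after Day 3 remains in the Per-Protocol Population but contributes nothing to later treatment visits.

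**The concern.** Under this rule, whether a later viral-load value exists can depend on the viral load itself. The decision is one of opinion, taken in an open-label trial. If the subjects removed are those doing worse than their group, the mean and median at later visits describe the remaining, better-responding subjects and overstate the decline. If groups differ in how often the rule is used, the comparison between groups moves as well. Optional replacement can restore the number contributing at a visit, so a reader could not see the loss from the count.

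There is no formal pharmacodynamic test. What is at stake is the reported size of activity at later visits, which in this pilot is the planned statement of activity.

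**Working it through.** The plan has no figure to reproduce. Section 8.7 states that nothing is assumed about effect or variability. The calculation below shows scale only.

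**Inputs from the documents:** up to 75 subjects (section 4) and four groups (Protocol Summary, Study Design).

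**Assumed inputs:**
- Equal split, 75/4 = 18.75 per group.
- Metric is log10 change from baseline (section 8.6 speaks only of levels).
- True mean μ = −1.0. Section 1.1 reports a drop of about 1 log or more in three of five treated subjects.
- SD 0.75 to 1.0.
- Everyone above a cut c is removed.
- The later value has the same mean and SD as the triggering value, with correlation ρ between them.

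**Formulas.** With z = (c − μ)/SD and P the share above c:
- mean of those removed at the trigger: E = μ + SD·φ(z)/P
- their later mean: E′ = μ + ρ(E − μ)
- mean of those kept: (μ − P·E′)/(1 − P)
- bias = μ − mean of those kept; a positive value favours the drug.

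**Main case, c = +0.5 log above baseline, ρ = 1:**
- SD 0.75: z = 2.0, P = 0.0228, E = 0.780; kept mean = (−1 − 0.0228 × 0.780)/0.9772 = −1.041; bias 0.041.
- SD 1.0: z = 1.5, P = 0.0668, E = 0.939; kept mean = (−1 − 0.0668 × 0.939)/0.9332 = −1.139; bias 0.139.
- Removed per group: 0.0228 × 18.75 = 0.4 and 0.0668 × 18.75 = 1.3 subjects.
- The median shifts by 0.02 and 0.08.

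**Variations:**

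| Setting | SD 0.75 | SD 1.0 |
|---|---|---|
| c = +0.5, ρ = 0.7 | 0.029 | 0.097 |
| c = +0.5, only half of those above c removed, ρ = 1 | 0.021 | 0.067 |
| c = +0.5, μ = −1.5, ρ = 1 | 0.009 | 0.055 |
| c = 0 (everyone above baseline), ρ = 1 | 0.135 | 0.288 |

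**Against sampling error.** The standard error of a group mean is 0.75/√18.75 = 0.173 or 1.0/√18.75 = 0.231. The first two fixed-cut cases (c = +0.5, μ = −1.0, all removed, ρ = 1 or 0.7) span 0.029/0.173 = 0.17 to 0.139/0.231 = 0.60 of one standard error. Only the extreme case at SD 1.0 exceeds one (0.288/0.231 = 1.25).

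**Rebounds that stay below baseline.** A simulation with nadir mean −1.0 or −1.5, the same SDs, and an exponential rebound of mean 0.3 or 0.5 removed subjects who rebounded by at least 1 log but stayed below baseline. That takes out 1.3 to 7.0% of subjects, with bias −0.010 to +0.024.

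**One subject.** In a group of 19 with mean −1.0, the kept mean after losing a subject at y is (−19 − y)/18. For y = +0.5 it is −1.083, a shift of 0.083 in favour of the drug. For y = −2.0 it is −0.944, a shift of 0.056 against.

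**The case against.** **The adverse-event route.** Section 7.1 counts any adverse change from baseline as an adverse event, including clinically significant laboratory abnormalities, and requires follow-up to resolution: "This may require obtaining clinical blood samples for appropriate laboratory tests until their values return to baseline levels". A rise above baseline bad enough to end participation fits that wording. Section 7.2 could then apply, and section 8.4.1 would list and summarise by group the adverse events that led to withdrawal. The case least likely to qualify, a rebound still below baseline, is the one with almost no bias. This stands as partial cover, so a reader who inferred that removed subjects can never be followed would go too far. It does not close the gap: no text classes an HDV rise as an adverse event, and section 7.2 concerns stopping drug rather than leaving the trial.

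**Other safeguards.** The investigator may add licensed drugs instead of removing the subject. Section 1.2 promises close watching of flares after EBP-994 ends. The four-week post-treatment visit may give one later value. None is tied to this rule, and none fills the later treatment visits.

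**Follow-up would not recover the loss.** Values after a stop are off drug, where section 1.1 reports rebound, or on interferon. They are not on-treatment activity, and a summary that excludes them is today's observed-only summary. This is correct, and it is why the fix counts failures beside the means.

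**The effect is small and rests on assumptions.** This also stands. The rule is permissive, the study is a descriptive pilot, and listings and graphs show each failure up to removal.

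**Conclusion.** The concern holds as a minor fix. Followed as written, the plan allows loss of later values that depends on the outcome, and no planned pharmacodynamic summary accounts for it. The illustrative bias is about 0.03 to 0.14 log10 in favour of the drug if everyone more than 0.5 log above baseline is removed, which is under one standard error per group. It rests on the assumed mean, SD, cut, correlation, equal split and log scale.

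A reader might infer three stronger conclusions that the documents do not support:
- **That the bias always favours the drug.** It does so only when those removed lie above the group mean. It is near zero or reversed for rebounds that stay below baseline.
- **That it is large.** Losing 4 of 19 subjects at +0.5 while the other 15 average −2.0 would turn a full mean of −1.47 into −2.00, but nothing in the documents supports such a removal rate or gap.
- **That these subjects leave the analysis population.** Those removed after Day 3 stay in the Per-Protocol Population, and only their later values are missing.

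**What to change.** 1. In the Protocol Summary (Safety), section 3 and section 7.3, reword the rule as a stop of study drug, still at the investigator's discretion.
2. Extend the section 7.2 follow-up sentence to these subjects, with HDV RNA at the visits already scheduled. Flag values taken after EBP-994 is stopped or after interferon is started. Report off-drug values for safety and rebound; they do not themselves remove the bias.
3. In section 8.6, report by group and visit the number contributing, the number stopped for a viral-load increase, and any replacements.
4. In section 8.6, add the proportion with at least a 1 log10 drop from baseline, among Per-Protocol subjects whose planned treatment reaches that visit (planned durations run from 4 to 48 weeks). Count viral-load stops as failures at all later planned treatment visits, whether or not measured. Show values missing for other reasons as a separate count.

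A numeric guide to what rise is unacceptable, like the one section 1.2 gives for an HBV flare, is optional and not needed for this fix.

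The cost is protocol wording, a few extra attended visits, and later summaries that may look slightly less favourable.

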## **4 ELIGIBILITY CRITERIA**

Up to 75 subjects chronically infected with HDV genotype 1 will be enrolled at a single University study site.

### ***4.1 Inclusion Criteria***

A subject may be included in this study if he/she meets all of the following criteria:

1. Males or females, 18 to 65 years of age who are diagnosed with HDV by PCR
2. Chronic hepatitis D infection, genotype 1, documented by a positive anti-HDV Ab test at least of 6 months duration and detectable HDV RNA by PCR within 3 months to study entry

3. Liver biopsy within the last two (2) years (biopsy can be done at the Screening Visit)
4. Positive viral load of >100,000 copies/mL as measured by quantitative PCR
5. Electrocardiogram (ECG) shows no acute ischemia or clinically significant abnormality and a QT/QTc interval <450 milliseconds - using Bazett's correction:  $QTc = QT/RR^{0.5}$  (ICH Guidance E14 Clinical Evaluation of QT/QTc Interval Prolongation and Proarrhythmic Potential for Non-Antiarrhythmic Drugs)
6. Females of childbearing potential (intact uterus and within 1 year since the last menstrual period) should be non-lactating and have a negative serum pregnancy test. In addition, these subjects should agree to use one of the following acceptable birth control methods throughout the study:
  - a. abstinence
  - b. surgical sterilization (bilateral tubal ligation, hysterectomy, bilateral oophorectomy) six months minimum
  - c. IUD in place for at least six months
  - d. barrier methods (condom or diaphragm) with spermicide
  - e. surgical sterilization of the partner (vasectomy for six months)
  - f. hormonal contraceptives for at least three months prior to the first dose of study drug
7. Willing and able to comply with study procedures and provide written informed consent

## **4.2 *Exclusion Criteria***

A subject will be excluded from this study if he/she meets any of the following criteria:

1. Participation in a clinical trial with or use of any investigational agent within 30 days of Study Visit 1
2. Patients co-infected with HIV
3. Patients with screening tests positive for HCV, or anti-HIV Ab
4. History of decompensated cirrhosis within the past year.
5. Active jaundice defined by total bilirubin >2.0 excluding Gilbert's

6. INR  $\geq 1.5$
7. Eating disorder or alcohol abuse within the past 2 years, excessive alcohol intake ( $>20$  g per day for females (1.5 standard alcohol drinks) or  $>30$  g per day for males (2.0 standard alcohol drinks) (a standard drink contains 14 g of alcohol: 12 oz of beer, 5 oz of wine or 1.5 oz of spirits) (1.0 fluid oz (US) = 29.57 ml), or if in the opinion of the investigator, an alcohol use pattern that will interfere with the study conduct
8. Drug abuse within the last six months with the exception of cannabinoids and their derivatives
9. Patients with absolute neutrophil count (ANC)  $<1500$  cells/mm^3; platelet count  $<100,000$  cells/mm^3; hemoglobin  $<12$  g/dL for women and  $<13$  g/dL for men; abnormal TSH, T4, or T3 or thyroid function not adequately controlled; or serum creatinine concentration  $\geq 1.5$  times upper limit of normal (ULN)
10. History or clinical evidence of any of the following:
  - a. variceal bleeding, ascites, hepatic encephalopathy, CTP score  $>6$ , decompensated liver disease or any other form of non-viral hepatitis
  - b. immunologically mediated disease (e.g., rheumatoid arthritis, inflammatory bowel disease, severe psoriasis, systemic lupus erythematosus) requiring more than intermittent nonsteroidal anti-inflammatory medications for management or that requires frequent or prolonged use of corticosteroids (inhaled asthma medications are allowed)
  - c. any malignancy within 3 years except for basal cell skin cancer
  - d. significant or unstable cardiac disease (e.g., angina, congestive heart failure, uncontrolled hypertension, history of arrhythmia)
  - e. chronic pulmonary disease (e.g., chronic obstructive pulmonary disease) associated with functional impairment
  - f. severe or uncontrolled psychiatric disease, including severe depression, history of suicidal ideation, suicidal attempts or psychosis requiring medication and/or hospitalization
11. Patients with a body mass index  $>30$  kg/m^2
12. Concomitant drugs known to prolong the QT interval
13. Concomitant use of immunosuppressive or immune modulating agents

14. Patients with any serious or condition that, in the opinion of the investigator, would preclude evaluation of response or make it unlikely that the contemplated course of therapy and follow-up could be completed or increase the risk to the subject of participation in the trial

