### Study Design

This study is a phase II, randomized, open-label study up to 48 weeks of treatment with EBP-994 alone, or in combination with Norvir® and/or Pegasys® in subjects chronically infected with HDV genotype 1. The duration of the study for each subject will last approximately 11-55 weeks (up to three week screening period, 4-48 week treatment period and four week safety follow-up period. The duration of the entire study is anticipated to be approximately 45 months (first subject in to last subject out). The investigator is free to initiate licensed medications at any time point and decrease the dose of EBP-994 if deemed warranted for GI side effects.

This study will explore EBP-994 in four groups of treatments:

Group 1: EBP-994 (up to 600 mg daily dose) monotherapy

Group 2: EBP-994 (up to 200 mg daily dose) in combination with Norvir®

Group 3: EBP-994 (up to 600 mg daily dose) in combination with Pegasys®

Group 4: EBP-994 (up to 150 mg daily dose) in combination with Norvir® and Pegasys®

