Given the aggressive nature of the hepatitis seen in HDV infection, agents are needed that can help mitigate the disease by directly interfering with the virus life-cycle. An important interaction between HDV and HBV proteins has been shown to depend on the presence of the last four amino acids of the large delta antigen, comprising a CXXX box motif, where C represents cysteine and X denotes any other amino acid. This amino acid sequence is required for the protein to be post-translationally modified by farnesyltransferase (FT), an enzyme which covalently attaches a prenyl lipid (farnesyl) to the cysteine of the CXXX box as depicted in Figure 1 (15,16). Prenylation of HDV results in the addition of farnesyl to the delta antigen. Inhibiting the action of FT could result in compromised HDV particle production since the unprenylated large delta antigen of HDV cannot associate with HBV antigens to form an infective HDV virion. In addition, the use of FT inhibitors (FTIs) could subvert the ability of the virus to develop resistance since the drug targeted locus does not lie within the viral genome but is a host function. Most importantly, host cells display a tolerance in the presence of prenylation inhibition by FTIs through the use of alternative prenylation pathways while HDV cannot use alternative pathways (17,18).

**Figure 1** The Mevalonate Pathway

Eiger BioPharmaceuticals, Inc. (Eiger BioPharmaceuticals) is developing EBP-994 as an investigational new drug for the treatment of hepatitis D virus (HDV) in patients chronically infected with HDV. EBP-994 is an orally active tricyclic farnesyltransferase inhibitor (FTI) initially developed as lonafarnib (aka SCH 66336) by Schering-Plough, now Merck. It has been studied in over 2000 patients within the context of over a dozen clinical studies, including three Phase I (pharmacokinetic, metabolic distribution, drug-drug interaction) healthy volunteer studies and nine Phase I, II and III studies in patients with advanced malignancies in an attempt to inhibit farnesylated ras-mediated cancers. In patients with advanced cancers (blast crisis and acute leukemia), EBP-994 has been given for up to 120 days with the MTD determined to be 200-300 mg PO BID, with TEAEs being diarrhea and nausea.

[figure not shown]

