CYP 3A (3A4 and 3A5) is responsible for the oxidative metabolism of EBP-994 (29, 31). Studies of CYP inhibition indicate that the CYP3A4 IC50 = 10.2  $\mu\text{g/mL}$  and CYP2C9 IC50 = 16  $\mu\text{g/mL}$  (24), showing that the one-half maximal inhibition is achieved at three to five times the mean human plasma Cmax (2.8  $\mu\text{g/mL}$ ) at 200 mg BID (46, 47, 48). Preincubation of human liver microsomes for 15 min with EBP-994 decreased the IC50 for inhibition of CYP3A4, suggesting a metabolism-based inhibition. In vitro inhibition of activity of other CYP enzymes (1A2, 2C19, 2D6) by EBP-994, however, does not appear to occur to an extent likely to suggest a risk of adverse events in humans.

In ancillary pharmacology studies in rats, EBP-994 was well tolerated over the oral dose range of 30 to 300 mg/kg. It was devoid of gastric ulcerogenicity and adverse effects on CNS function, but exhibited moderate inhibition of GI motility at high doses ( $\geq 100$  mg/kg). Clinical findings consistent with a decrease in GI motility have not been observed with EBP-994. Urine chemistry parameters showed a decrease in sodium and potassium excretion at 300 and 500 mg/kg and a reduction in creatinine clearance at 500 mg/kg. At doses of 500 mg/kg orally, rats were moribund and displayed a variety of adverse effects. Repeated oral

dosing of EBP-994 to monkeys at 60 mg/kg for 7 days caused diarrhea, emesis, weight loss, thrombocytopenia and an elevation of AST.

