## **5.3 Concomitant Medications**

All drugs that are listed as excluded in the Exclusion Criteria should not be initiated during the study unless prior approval has been received from the Medical Monitor. Check the prescribing information of Norvir® and Pegasys® before initiating any concomitant medication.

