## **6.2 Study Visit 2 (Day 1) - Treatment Period**

This Study Visit marks the beginning of the twenty-four weeks treatment Period in which subjects will receive EBP-994 treatments (EBP-994 alone or in combination with Norvir® and/or Pegasys®). Subjects will be admitted to the unit on the morning of Day 1 in a fasted

state (nothing to eat or drink except water) and will receive a standard breakfast between 45 - 30 minutes prior to scheduled dosing time.

The following evaluations and procedures will be performed at Study Visit 1 (see Appendix A for summary):

1. Brief physical examination pre-dose (performed by a physician, nurse practitioner, physician's assistant or nurse). This includes weight and vital signs as well as HEENT, heart, lungs, abdomen and lower extremity.
2. Vital signs pre-dose and after the post-dose ECG (BP after being seated for 5 minutes, pulse, respiratory rate and temperature)
3. Concomitant medications will be recorded
4. Adverse events will be recorded
5. 12-Lead ECG
6. Randomization

Subjects will be randomized to one of the following groups:

Group 1: EBP-994 (up to 600 mg daily dose) monotherapy  
Group 2: EBP-994 (up to 200 mg daily dose) in combination with Norvir®  
Group 3: EBP-994 (up to 200 mg daily dose) in combination with Pegasys®  
Group 4: EBP-994 (up to 200 mg daily dose) in combination with Norvir® and Pegasys®

7. Laboratory studies (Pre-Dose) (non-fasting):
  - a. Serum chemistry panel, including liver function tests and albumin
  - b. Complete blood count (CBC with differential and platelet count)
  - c. Quantitative PCR for HDV viral load
  - d. Blood samples (plasma and serum) for viral mutation analysis, resistance phenotyping, and analysis of drug mechanism and treatment response. These analyses include molecular and genetic analysis of drug mechanism, viral/host factors influencing treatment response (e.g. genotype and subgenotype analysis, quasispecies analysis, determination of drug and potential metabolite levels in plasma).
  - e. Urinalysis
  - f. Urine pregnancy test (child-bearing females only)

- g. Blood sample for monitoring immunologic changes in peripheral blood mononuclear cells (PBMC).
- 8. Pharmacokinetic blood samples (at the following time points: 0-pre-dose, post dose: 15 min, 30 min, 60 min, 90 min, 2h, 2.5 h, 3 h, 4 h, ,6 h, 8, 10, 12 h) (for those subjects participating in the PK portion of this trial)
- 9. Dosing Instructions:  

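### Neither exclusion list bars strong CYP3A inhibitors or inducers as such, so a subject already taking one can be randomised to EBP-994 at up to 300 mg BID, the stated MTD

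*Combined protocol and SAP*

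**What the plan says.** - **Metabolism.** Section 1.2 (Preclinical Safety Summary): "CYP 3A (3A4 and 3A5) is responsible for the oxidative metabolism of EBP-994". The same section describes extensive metabolism, with little drug excreted unchanged.
- **Entry.** Section 4.2, items 12 and 13, exclude "Concomitant drugs known to prolong the QT interval" and "Concomitant use of immunosuppressive or immune modulating agents". Items 11 and 12 of the Protocol Summary list are the same. Other items remove recent users of investigational agents and subjects with HIV. Item 14 (Summary item 13) leaves the investigator discretion over serious conditions that raise a subject's risk; it names no drug. Neither list mentions CYP3A.
- **Screening.** Section 6.1 lists concomitant medications but sets no stopping or washout rule for CYP3A drugs. The screening window is 21 days.
- **During the study.** Section 5.3: "All drugs that are listed as excluded in the Exclusion Criteria should not be initiated during the study", unless the Medical Monitor has approved. It then adds: "Check the prescribing information of Norvir® and Pegasys® before initiating any concomitant medication".
- **Licensed medications.** The Protocol Summary (Study Design, and the dosing plan), Section 3 and Section 7.3 leave the investigator free to start these whenever he or she chooses.
- **Dose.** Section 6.2: "Group 1: EBP-994 (up to 600 mg daily dose) monotherapy". The Protocol Summary has "Group 3: EBP-994 (up to 600 mg daily dose) in combination with Pegasys", whereas Section 6.2 caps Group 3 at 200 mg daily. Section 2 names 300 mg BID as a study dose.
- **MTD.** Section 1 describes use in advanced cancer "with the MTD determined to be 200-300 mg PO BID". Section 1.2 (Clinical Safety Summary) gives 300 mg BID.

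**The concern.** The protocol identifies the enzyme that clears the drug and then writes no rule about co-medications that block or induce that enzyme. What is at stake is the individual subject, in two directions.

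With an inhibitor on board, exposure could rise above what the assigned dose usually gives. In Group 1 that dose can already be the MTD, and Section 1.2 describes the diarrhoea as dose related. Early visits, laboratory review, dose reduction and withdrawal are all available, but they act after toxicity has appeared. An entry criterion acts before it.

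With an inducer on board, exposure could fall. Section 1.1 reports that viral-load change tracked individual drug levels and that levels at 100 mg BID appeared suboptimal. A subject assigned a higher dose could be brought back towards that level without anyone intending it.

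**Working it through.** **Step 1: which rule reaches a strong CYP3A inhibitor or inducer?**

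| Situation | Rule | Does it reach the drug? |
|---|---|---|
| Already taken at Screening | 4.2 items 12 and 13 | Only if the drug also prolongs QT or is immunosuppressive or immune modulating |
| Already taken at Screening | 4.2 items 2 and 3 (HIV) | Only by removing subjects on HIV treatment |
| Already taken at Screening | 4.2 item 14 | By discretion only; it concerns a condition, not a drug |
| Already taken at Screening | 5.3, both sentences | No; both concern starting a drug |
| Started after Day 1 | 5.3, approval sentence | Only if the drug is in a class already barred |
| Started after Day 1 | 5.3, label check | In part: two partner labels, in all groups, with nothing on EBP-994 itself |

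The clear gap is the third to fourth rows taken together: a drug outside the barred classes that is already in use at entry. No mandatory rule stops that subject from being randomised.

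**Step 2: the dose such a subject can receive.** 600 mg daily / 2 = 300 mg BID. This equals the MTD in Section 1.2 and the top of the range in Section 1. It applies to Group 1 in both places where groups are defined, and to Group 3 only under the Protocol Summary.

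**Step 3: can the effect be sized?** No. The plan gives no figure to reproduce. It reports no exposure ratio for EBP-994 with an inhibitor or inducer, and no prevalence of such drugs. What can be shown is how large a change would matter, on the protocol's own doses, under an assumed relation: exposure proportional to dose^b. The documents do not give b for humans. The range below is an assumption. It runs to 1.5 because Section 1.2 reports signs of metabolism-based CYP3A4 inhibition by EBP-994, so more-than-proportional exposure cannot be ruled out.

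| Change needed | Formula | b = 0.8 | b = 1 | b = 1.2 | b = 1.5 |
|---|---|---|---|---|---|
| Fall from 300 to 100 mg BID exposure | 1 - (100/300)^b | 58.5% | 66.7% | 73.2% | 80.8% |
| Fall from 200 to 100 mg BID exposure | 1 - (100/200)^b | 42.6% | 50.0% | 56.5% | 64.6% |
| Rise from 200 to 300 mg BID exposure | (300/200)^b | 1.38-fold | 1.50-fold | 1.63-fold | 1.84-fold |

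These are illustrative break-even values. They do not predict what any co-medication would do.

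**Step 4: what under-exposure would mean.** Section 1.1 reports viral-load reductions in all treated patients at 100 mg BID, with about 1 log or more in three of five. Section 3 measures HDV RNA at all visits. Falling to the 100 mg BID level therefore means reduced activity, which monitoring may detect.

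**The case against.** The strongest reply is that this is a mechanism without a measured hazard. Section 1 mentions a drug-drug interaction study in healthy volunteers. Its results are not reproduced, and they could support a rule or undercut it. Screening already lists co-medications, the two barred classes and the HIV exclusion remove some of the relevant drugs, and item 14 lets an investigator refuse a subject at risk. After entry, subjects are seen often and doses can be cut.

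Most of this stands, and it limits the weight of the point. It does not close the gap, because item 14 is discretionary and the remaining controls act after dosing has begun.

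Four stronger readings are tempting, and the documents do not support them:

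- **That any rise at 300 mg BID means toxicity.** An MTD is a dose set across patients whose exposures vary. The average exposure at that dose is not an individual threshold.
- **That a subject on an inducer would lose the effect for 48 weeks.** Step 4 shows why not. In an open-label study the investigator can also add licensed treatment.
- **That group results would be distorted.** PK sampling is optional (Section 3), so the number of subjects contributing an AUC is unknown and a shift in the group mean cannot be computed. In the Day 28 versus Day 1 comparison, a stable co-medication acts on both days and largely cancels.
- **That the lower caps with Norvir measure the interaction.** The Group 1 cap is 600/200 = 3 times the Group 2 cap, but the protocol does not say why the caps differ.

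**Conclusion.** The gap is real and narrow. As written, the plan allows a subject who already takes a strong CYP3A inhibitor or inducer, outside the QT-prolonging, immunosuppressive or immune modulating, and HIV-related exclusions, to be randomised to EBP-994 at up to its stated MTD. That conclusion rests on the text of both exclusion lists and Section 5.3 and needs no numerical assumption.

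The size of the harm is not established. The break-even values depend on an assumed exponent, and neither the interaction effect nor its frequency is given. This is an inexpensive improvement that the sponsor should make, not a demonstrated safety failure.

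**What to change.** 1. Add to Section 4.2 and to the Protocol Summary list an exclusion for use of strong CYP3A inhibitors or inducers at Day 1, other than assigned Norvir. The sponsor's clinical pharmacology group should set the drug list and a washout that fits the 21-day screening window. At entry the exclusion governs, and continuation by approval is not an option.
2. Extend Section 5.3 so that after entry these drugs may be started only with Medical Monitor approval. Refer there to EBP-994's own interactions as well as to the two partner labels.
3. Make the sentences on starting licensed medications (Protocol Summary, Study Design and dosing plan; Sections 3 and 7.3) subject to Section 5.3. This is required, because otherwise they contradict step 2.

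The cost is one amendment that touches these passages. No new procedure is needed, because co-medications are already recorded at Screening and at every visit. A few candidates would be excluded or would wait through a washout; the documents do not allow that number to be estimated.
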